## D.3. Analysis of Time to Event Data

This section describes the methods for analyzing time-to-event endpoints, for example, time to:

- achieve 1g/dL increase in Hb in Year 1 (CI-0014)
- first rescue therapy (by series of definitions)
- first RBC transfusion
- first ESA use (aside from control arm medication not specified as rescue)
- progression of chronic kidney disease (CKD).
- study discontinuation

Time-to-event distributions will be estimated using the Kaplan-Meier product-limit method and log rank test.

The hazard ratio and corresponding 95% confidence interval for the comparison of vadadustat to darbepoetin alfa will be estimated using a Cox proportional hazards model, with treatment group and other predictors as covariates. Analyses in the randomized population will be stratified by the stratification factors; analyses in subgroups will be conducted similarly. The predictor variables (&PREDVAR. in [Exhibit D 3](#)) for hemoglobin-related events are baseline ESA dose (three

Statistical Analysis Plan AKB-6548-CI-0014 and AKB-6548-CI-0015

levels specified in [Section 11](#)) and continuous baseline Hb. For CKD progression, the predictor variable is continuous baseline eGFR.

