## 2.6 Sample Size

The planned sample sizes are approximately 925 subjects per arm for both Study CI-0014 and Study CI-0015. The sample sizes have been selected to contribute adequate MACE for a pooled analysis that will take place using the results from both studies. See Sections 2.7 and 2.8 for the operating characteristics of the studies, given these samples sizes, with respect to the stand-alone efficacy analysis to be performed on change in Hb and the pooled MACE analysis.

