## 2.8 Safety

The primary safety endpoint is the time from the first dose date to the first adjudicated MACE (defined as all-cause mortality, nonfatal myocardial infarction, or nonfatal stroke).

The primary safety analysis will include all first events that accrue over the pair of PRO2TECT studies. The sample size for the MACE endpoint is based on a 2-sided 95% confidence interval for the hazard ratio (HR) (vadadustat/darbepoetin alfa) and a noninferiority margin of 1.25 (upper bound of the 95% confidence interval) for FDA decision making. Under the assumption that the MACE rate is the same in the 2 groups (i.e., the HR =1), 631 subjects with MACEs will be required in the 2 trials combined to have 80% power to establish noninferiority. If the HR is 0.95 favoring vadadustat, the power will be above 90%. Based on a noninferiority margin of 1.30 for EMA decision making, the power will be above 90% under the assumption that the HR is 1.

Additional safety presentations are described below ([Section 7](#) and [Section 10](#)).

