### 6.3.9 Rescue Therapy: Series of Definitions

Rescue will be defined from narrow to broad, based on the type, timing, intensity, and reason for treatment. These treatments may be considered rescue therapy for anemia secondary to chronic kidney disease: ESA medication, and RBC transfusion.

The possible reasons for such treatments include:

- Investigator-ordered rescue (per protocol for worsening of anemia),
- Adverse events (unrelated to anemia),
- Maintenance during prolonged interruption of study treatment, and
- Inadvertent use (at hospital or dialysis center).

If a given therapy starts the same day as permanent discontinuation of study drug, then that therapy will be considered on treatment for rescue definitions.

For the vadadustat arm, any use of ESA may be considered rescue. For the control arm, the study drug itself is an ESA and so is not necessarily rescue, yet change to another ESA may be considered rescue. Because darbepoetin alfa is titratable, increase in dose is not considered rescue unless the investigator specifically designates it as such; however, increases in dose relative to last dose will be characterized in three categories by percentage increase: <50%,

Statistical Analysis Plan AKB-6548-CI-0014 and AKB-6548-CI-0015

$\geq 50\%$  and  $< 100\%$ , and  $\geq 100\%$ . Subjects will be presented by their maximum category of increase within each of the four analysis time periods in Year 1 (see [Section 5.1](#)). All ESA use will be converted to IV epoetin alfa equivalents.

The CRFs collect reasons for ESA medication and RBC transfusion. The series of rescue definitions are defined as follows:

- Narrow: Rescue for worsening anemia with ESA medication or RBC transfusion defined in [Section 6.3.7](#) and [Section 6.3.8](#), not starting after permanent study treatment discontinuation.
- Broad-on-treatment: Any exposure to ESA medication (aside from darbepoetin alfa not designated as rescue in the control arm) or RBC transfusion for any reason not starting after permanent study treatment discontinuation.

In addition to the sensitivity analyses ([Section 9.1.4](#)), the report will include a summary of the incidence, timing, duration, intensity, and frequency for each definition of rescue, including a Kaplan-Meier plot of time to first rescue.

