### **Exhibit D 3. SAS Code for Time to Event Data Analysis**

---

```
*** compute median times with KM product limit method;

proc lifetest data=&TTEDAT. alphaqt=0.05 conftype=LOGLOG confband=ALL
timelim=OBSERVED outsurv=RATES timelist= 0 24 36 40 52 reduceout;

    by TRT;

    time AVAL * CNSRN(1);

run;

*** compute hazard ratios with Cox proportional hazards model;

proc phreg data=TTE;

class TRT;

model AVAL * Status(0) = TRT HB_BL STRAT1 STRAT2 &PREDVAR. / ties=Efron;

hazardratio 'Cox proportional hazard' TRT;

ods output HazardRatios=hazard;

run;
```

---

For laboratory-based time-to-event endpoints, subjects who do not experience an event will be censored on the date of the last evaluable assessment of the laboratory parameter. For time to progression of CKD, subjects who do not experience CKD progression will be censored on date of last visit with no kidney transplant or dialysis.

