## 2.2 Method of Assigning Subjects to Treatment Groups

Subjects will be randomized 1:1 using permuted block randomization. Randomization will be stratified in each of the four studies by the following:

- Geographic region
  - United States (US)
  - European Union (EU)
  - Rest of World (ROW)
- New York Heart Association congestive heart failure (CHF) class
  - Class 0 or I
  - Class II or III
- Baseline Hb (g/dL)
  - <9.5 versus  $\geq$ 9.5 for CI-0014 and 0016
  - <10 versus  $\geq$ 10 for CI-0015 and 0017

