### 2.5.1 The PRO2TECT studies (CI-0014 and CI-0015)

The primary safety analysis will be based upon all first events that accrue over the two PRO2TECT trials. If the noninferiority (NI) margin is 1.25 and the event rate is the same in the two treatment groups (i.e., the hazard ratio (HR) is 1.0), then 631 events are needed to establish NI with 80% power; 631 events yields more than 90% power to exclude an NI margin of 1.30. If the HR is 0.95 favoring vadadustat, the power is above 90% when the NI margin is 1.25.

Justification for the NI margin of 1.25 for FDA decision making and 1.30 for EMA decision making is provided in [Appendix C](#).

An annual MACE rate of 10% is anticipated. This rate is based on a comprehensive review of available epidemiology and prospective clinical studies in NDD-CKD. Therefore, a projected total of 3700 subjects will be enrolled in studies CI-0014 and CI-0015. With 1850 subjects planned per treatment group in studies CI-0014 and CI-0015 and a planned accrual period of approximately 20 months, and up to 36 months of follow-up (with expected mean follow-up about 2 years), the number of MACE in each study will be a function of the actual pattern and size of enrollment as well as the duration of follow-up.

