## **4 STATISTICAL ANALYSIS**

For each subject in the four studies, duration of follow-up will be calculated as the number of days between date of first dose date and last contact date during the study plus one. For each outcome, the number of events that occur during that period may be included in the analysis. The event rate will be calculated as the number events divided by the duration of at-risk follow-up in

person-years. Survival analyses will include only the first event for each subject in that period. For each type of event, the event rate will be summarized by treatment group for each study and for each pair of studies (CI-0014/15 and CI-0016/17).

For each type of event that includes all-cause death (including the primary endpoint), the method of analysis for each pair of studies will be a Cox regression with the randomized treatment assignment as a predictor. The models will be stratified by study. Subjects without an event will be censored at their last study contact (visit or telephone contact) at which all components of the outcome were assessed. Deaths that occur between withdrawal of consent or loss to follow up and the global study completion date (GSCD) and that are identified, prior to database lock, through public records will be included in the analyses as an event. The models will use other covariates as well, as described below.

For all other events, analyses will use competing risk methods. These methods produce valid estimates of the marginal probability of the event in case other events preclude observation of the event of interest. For each pair of studies, the models include the randomized treatment assignment as a predictor and, should a competing event not occur, subjects will be censored on their last study contact (visit or telephone contact) at which all components of the outcome were assessed. The models will use other covariates as well, as described below. Models for the overall analysis of PRO2TECT and of INNO2VATE will also stratify by study. [Appendix A](#) provides SAS code for the competing risk analysis.

The studies will enroll subjects from many centers; however, most centers will have small sample sizes. Therefore, as described in the general SAPs for PRO2TECT and INNO2VATE, no center-specific analyses are planned.

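### Kaplan-Meier for time to CKD progression censors deaths, so the incidence read from it is too high: by under 1 SE up to week 52, and by about 0.4 to 2.7 SE at 2 to 2.5 years under assumed rates

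*SAP*

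**What the plan says.** SAP Appendix D.3 covers, among others, time to first rescue, first RBC transfusion, first ESA use and CKD progression. The method is the same for all: "Time-to-event distributions will be estimated using the Kaplan-Meier product-limit method and log rank test", with a Cox model for the hazard ratio. SAP 6.3.9 adds a summary of rescue "including a Kaplan-Meier plot of time to first rescue".

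For CKD progression the text after Exhibit D 3 gives the censoring rule: "subjects who do not experience CKD progression will be censored on date of last visit with no kidney transplant or dialysis". A death without progression falls under that rule. SAP 6.3.6 defines progression by chronic dialysis, transplant, confirmed eGFR below 15, or a confirmed fall of at least 40%. Death is not a component.

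For transfusion, ESA use and rescue no censoring rule is written. The `PROC LIFETEST` step in Exhibit D 3 has a single censoring code and no event code for death, so censoring at death is implied only.

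The exhibit outputs Kaplan-Meier rates at 0, 24, 36, 40 and 52 (taken here as weeks) and computes medians. SAP Table 3 analyses CKD progression over the whole study. SAP 6.3.7 and 6.3.8 do the same for first transfusion and first ESA.

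The MACE SAP, Section 4, first deals with outcomes that include all-cause death and then says: "For all other events, analyses will use competing risk methods". Protocol 11.7.1 plots its Kaplan-Meier curves for comparable safety endpoints as time to the endpoint or death.

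**The concern.** A subject who has died can no longer progress, be transfused or be rescued. Censoring that subject assumes that he or she would have gone on to have the event at the same rate as the survivors. The quantity estimated is then the risk in a population in which nobody dies. A reader of the study report will take the curve as the percentage of patients who progressed, and that percentage is lower. The direction of the error is known, it grows with follow-up, and a larger sample does not remove it.

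Mortality here is not negligible: the programme plans on a MACE rate of 10% per year, and all-cause death is a MACE component. At stake are the absolute incidences and medians reported for CKD progression and, to a lesser degree, for transfusion, ESA use and rescue.

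**Working it through.** **The plan's own figure.** The documents give no incidence, median or standard error for these endpoints. The only time-to-event design figure is the number of MACE events (MACE SAP 2.5.1): margin 1.25, hazard ratio 1, two-sided 95% interval, 80% power. Schoenfeld: 4 × (1.960 + 0.842)² / (ln 1.25)² = 630.5, so 631 events, as stated. It does not bear on the present point beyond confirming the sizing inputs.

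**Inputs from the documents**
- Size (SAP 2.6): "The planned sample sizes are approximately 925 subjects per arm for both Study CI-0014 and Study CI-0015".
- Follow-up (MACE SAP 2.5.1): about 20 months' accrual, up to 36 months' follow-up, mean about 2 years. Modelled as administrative censoring uniform over 16-36 months (mean 26 months).

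**Assumptions, because the documents give no figure**
- Death: 3, 5, 7 or 9% per year, kept below the 10% MACE rate of which it is part.
- CKD progression: 10-40% per year.
- First transfusion, ESA or rescue: 3-15% per year.
- Constant hazards, λ for the event and μ for death; no loss to follow-up beyond the administrative censoring.

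**Formulas**
- 1-KM with deaths censored: 1 − exp(−λt)
- True cumulative incidence: λ/(λ+μ) × [1 − exp(−(λ+μ)t)]
- Greenwood SE: exp(−λt) × √{∫₀ᵗ λ du / [925 · exp(−(λ+μ)u) · G(u)]}, where G is the probability of not yet being administratively censored.

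**Example, λ = 0.20 and μ = 0.05**
- Week 52: 1 − e^(−0.20) = 18.1%; 0.8 × (1 − e^(−0.25)) = 17.7%. Excess 0.4 points; SE 1.28; ratio 0.34.
- 2 years: 1 − e^(−0.40) = 33.0%; 0.8 × (1 − e^(−0.50)) = 31.5%. Excess 1.5 points; SE 1.67; ratio 0.89.
- 2.5 years: 1 − e^(−0.50) = 39.3%; 0.8 × (1 − e^(−0.625)) = 37.2%. Excess 2.2 points; SE 1.98; ratio 1.09.

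A simulation of 2000 trials gave ratios of 0.35, 0.85 and 1.08 at these times.

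**CKD progression, full assumed range, per arm**

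| Time | Excess (points) | Excess / SE |
|---|---|---|
| Week 24 | 0.03-0.3 | 0.05-0.27 |
| Week 36 | 0.1-0.7 | 0.08-0.49 |
| Week 52 | 0.1-1.4 | 0.14-0.85 |
| 2 years | 0.5-4.1 | 0.38-2.22 |
| 2.5 years | 0.8-5.6 | 0.47-2.68 |

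**Transfusion, ESA use, rescue (3-15% per year).** The excess is 0.08-0.51 SE at week 52 and 0.21-1.31 SE at 2 years.

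**Medians.** With λ = 0.30 and μ = 0.05 the KM median is ln 2 / 0.30 = 2.31 years. Cumulative incidence reaches 50% at −ln(1 − 0.5 × 0.35/0.30) / 0.35 = 2.50 years. The KM median is about 10 weeks early, or 1.5 SE (SE 0.128 years). Across progression at 25-40% per year it is 3-30 weeks early (0.7-2.9 SE). At 20% per year or less it is at least ln 2 / 0.20 = 3.5 years, beyond the 36-month maximum. Medians for transfusion, ESA use and rescue are not reached.

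**Difference between arms.** With equal event and death rates the excess cancels. With λ = 0.20 in both arms and death at 5% against 6% per year, the 2-year excesses are 1.49 and 1.78 points. The distortion is 0.3 points against an SE of the difference of 2.4 points.

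**The case against.** Four arguments on the other side carry weight.

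- **The listed output times stop at week 52, where the excess is under 1 SE.** That is so. But CKD progression is analysed over the whole study, and its median, where one is reached, lies well past week 52.
- **Proportions are already handled for three of the endpoints.** SAP Table 3 and Appendix D.1 analyse receipt of any transfusion, any ESA rescue and any rescue therapy as binary outcomes with Mantel-Haenszel differences. Those are crude proportions, not 1-KM. A reader might infer that the planned percentages transfused or rescued are overstated; they are not. Only the curves are affected. CKD progression has no such companion analysis.
- **Kaplan-Meier with deaths censored validly estimates a net risk.** It does, if that is the target, but the SAP does not say that it is. The log-rank test and the Cox model with deaths censored are proper cause-specific analyses, so a reader who concludes that the treatment comparison is invalid goes too far.
- **The MACE SAP governs its own outcomes.** Its competing-risk rule does not extend to these endpoints, so this is an unexplained difference in practice within one programme, not two conflicting instructions for one endpoint.

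A reader might also infer a bias of about 4 SE. That needs every subject followed for a full 3 years at extreme assumed rates: with a binomial SE, 3.9 at progression 30% and death 9% per year. The staggered entry and roughly 2-year mean follow-up in the plan rule it out.

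**Conclusion.** The point holds for CKD progression: the plan censors deaths in a Kaplan-Meier estimate for an endpoint that death precludes, so the crude incidence is overstated and any median reached is too early. For first transfusion, ESA use and rescue it holds for the curves only, is smaller, and rests on the sample code because no censoring rule is written.

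The error grows from under 1 SE at every time listed in the exhibit to 0.4-2.2 SE at 2 years and 0.5-2.7 SE at 2.5 years for CKD progression. These figures depend on assumed constant death and progression rates, and lower rates would make them smaller.

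SAP 9.3 treats these endpoints as exploratory. The point is a cheap correction to the absolute figures and does not touch any primary, key secondary or MACE conclusion.

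**What to change.** In SAP D.3, SAP 6.3.9 and Exhibit D 3:

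- Report the cumulative incidence function, with death as the competing event, in place of 1-KM for CKD progression and for the first transfusion, ESA and rescue curves. In the code, give death its own status value and add `EVENTCODE=` to the `TIME` statement of `PROC LIFETEST`. Read any median from that curve.
- Keep the log-rank test and the Cox model with deaths censored, and label the hazard ratio as cause-specific.
- Write the censoring rule for first transfusion, ESA use and rescue. For rescue, state how permanent discontinuation of study medication is handled, since both definitions in SAP 6.3.9 exclude therapy that starts after it.

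The cost is a few sentences, one more event code and one code option. Death dates are already needed for the MACE analysis. The only visible effect is slightly lower reported percentages: in the worked example, 31.5% in place of 33.0% at 2 years.

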### **Exhibit D 3. SAS Code for Time to Event Data Analysis**

---

```
*** compute median times with KM product limit method;

proc lifetest data=&TTEDAT. alphaqt=0.05 conftype=LOGLOG confband=ALL
timelim=OBSERVED outsurv=RATES timelist= 0 24 36 40 52 reduceout;

    by TRT;

    time AVAL * CNSRN(1);

run;

*** compute hazard ratios with Cox proportional hazards model;

proc phreg data=TTE;

class TRT;

model AVAL * Status(0) = TRT HB_BL STRAT1 STRAT2 &PREDVAR. / ties=Efron;

hazardratio 'Cox proportional hazard' TRT;

ods output HazardRatios=hazard;

run;
```

---

For laboratory-based time-to-event endpoints, subjects who do not experience an event will be censored on the date of the last evaluable assessment of the laboratory parameter. For time to progression of CKD, subjects who do not experience CKD progression will be censored on date of last visit with no kidney transplant or dialysis.

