Refer to [Sections 7.4.1, Retesting](#) and [7.4.2, Rescreening](#) for further details regarding repeating laboratory measurements during the Screening period.

- **Point of care Hb:** Using HemoCue, Hb will be monitored throughout the study to determine if the dose of study medication (vadadustat or darbepoetin alfa) will be

adjusted, interrupted, or maintained as described in [Section 8.4.4 Dosing and Dose Adjustment Guidelines](#).

- Reticulocyte count: An automated reticulocyte count (both absolute and percent) will be performed at Baseline and at Weeks 4, 12, 28, and 52.
- Coagulation tests: Blood samples will be drawn at Baseline to assess the prothrombin time (PT), partial thromboplastin time (PTT), and international normalized ratio (INR).
- Folate and Vitamin B₁₂: A blood sample will be drawn at SV1 to assess the folate and Vitamin B₁₂ levels.
- Urine albumin-to-creatinine ratio (uACR): A random urine spot sample should be collected at the investigative site during the Baseline, Weeks 28, 52, 104, 156, 208, and EOT to assess the uACR. Subjects should refrain from heavy exercise 24 hours before the test.
- C-reactive protein (CRP): A blood sample for CRP will be collected at the Baseline, Weeks 28, 52, 104, 156, and EOT.
- Serum Chemistry: Blood samples to assess serum chemistry will be collected at SV1, Baseline, and twice annually at Weeks 28, 52, 76, 104, 128, 156, 180, 208, EOT. At all other noted visits in [Appendix A: Schedule of Activities](#), serum creatinine and eGFR will be performed only at Weeks 4, 8, 12, 20, 36, 44. The serum chemistry will include the following assays: sodium, potassium, bicarbonate, chloride, calcium, magnesium, phosphorus, glucose, creatinine, blood urea nitrogen (BUN), creatine phosphokinase (CPK), uric acid, albumin, total protein, and eGFR calculation.
Note: When a $\geq 50\%$ decline in eGFR from the Baseline value is observed, a repeat central laboratory measure should be performed within 30 to 60 days.
- Liver Function Tests: Blood samples to assess liver function will be collected at SV1, Baseline, Weeks 4, 8, 12, 16, 20, 24, 28, 36, 44, 52, 64, 76, 88, 104, 116, 128, 140, 156, 168, 180, 192, 208, and EOT. Liver function tests will include: total bilirubin, alkaline phosphatase, ALT/SGPT, AST/SGOT, and lactate dehydrogenase (LDH).

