### *Study CI-0015*

- Conversion and Maintenance Period (Weeks 0-52):
  - Weeks 0 to 23: conversion to study treatment for maintaining Hb
  - Weeks 24 to 36: PEP
  - Weeks 40 to 52: SEP

After Week 52, subjects in both studies will proceed to the following 2 periods:

- **Long-Term Treatment Period (Weeks 53-End of Treatment [EOT]):** continued treatment with study medication to assess long-term safety
- **Follow-up Period (EOT + 4 weeks):** post-treatment visit (either in person or by telephone) to assess safety

The duration of the trial will depend on how long it takes for a total of 631 adjudicated MACE to occur in the 2 studies combined. A separate SAP will describe the planned MACE analyses, including the method planned for pooling data from the 2 PRO2TECT studies.

The safety reporting period for a subject enrolled in this study begins upon randomization and ends at the final protocol-required study contact (visit or telephone), also known as a subject's end of study (EOS). In addition, the Investigator should report any adverse event (AE) that occurs after this period if he or she assesses it as possibly or probably related to the study medication.

According to the schedule of visits in the protocol, no laboratory assessments, physical exams, or other procedures are planned after the subject's permanent discontinuation of study medication, also known as EOT; however, AE and rescue therapy assessments, including monitoring for MACE endpoints, will continue until a subject's EOS.

The analysis time periods for efficacy divide the Correction/Conversion and Maintenance periods, Year 1 collectively, into four windows (see [Table 1](#)).

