### 6.3.6 Progression of CKD

Progression of chronic kidney disease (CKD) in both studies is defined as experiencing any of the following:

- Transition to chronic dialysis, or
- Receipt of a kidney transplant, or
- Estimated glomerular filtration rate (eGFR) <15 mL/min per 1.73 m^2 and confirmed by another measurement with a reduction of eGFR <15 mL/min per 1.73 m^2, which should be at least 28 days apart from the first reduction, or
- Reduction in eGFR of 40% or more from baseline (confirmed by second measurement at least 28 days later).
- The endpoint for analysis is time to progression of CKD. See [Coresh, 2019](#); [Heerspink, 2019](#); [Levey, 2014](#) for a description of the endpoint.

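### CKD progression is censored at the last visit rather than the last eGFR, so off-drug time counts as progression-free for two components that are no longer measured

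*SAP*

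**What the plan says.** SAP 6.3.6 defines progression of CKD by any one of four events. Two need no laboratory value: "Transition to chronic dialysis, or" or a kidney transplant. Two need confirmed eGFR: a value below 15 mL/min/1.73 m², with a second such value "which should be at least 28 days apart from the first reduction, or" a relative fall, worded as "Reduction in eGFR of 40% or more from baseline (confirmed by second measurement at least 28 days later". SAP Table 3 analyses the endpoint as time to event over the whole study.

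SAP Appendix D.3 gives two censoring rules in consecutive sentences. The general rule, for outcomes derived from a laboratory value, is that "subjects who do not experience an event will be censored on the date of the last evaluable assessment of the laboratory parameter". CKD progression then gets a rule of its own: "subjects who do not experience CKD progression will be censored on date of last visit with no kidney transplant or dialysis".

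On data after drug is stopped, SAP 2.2 states that "no laboratory assessments, physical exams, or other procedures are planned after the subject's permanent discontinuation of study medication", while adverse event, rescue and MACE follow-up continues to end of study. Protocol (Amendment 7-COL) 7.5.5.4 makes off-drug assessments flexible, and its preferred set contains no eGFR. Protocol 11.5 says the opposite: subjects who stop drug keep to the planned visits and assessments.

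Protocol 9.2.2 asks for an extra test when a 50% or greater "decline in eGFR from the Baseline value is observed, a repeat central laboratory measure should be performed within 30 to 60 days".

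**The concern.** A subject who has stopped drug can still be recorded as starting dialysis or receiving a transplant, but on the SAP 2.2 reading cannot be recorded as having a 40% fall or an eGFR below 15. Under D.3 that subject nevertheless stays in the risk set for the whole composite until the last visit, which may be a telephone contact. The person-time enters the denominator while part of the numerator is unobservable.

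The arm that stops drug more often gains more of this unobservable time, so its hazard is pulled down more. This is an open-label trial comparing a tablet with an injection, and discontinuation need not be equal. The comparison at stake is the SAP's only time-to-event renal comparison.

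The rule also departs from the SAPs' own practice: from the preceding sentence of D.3, and from section 4 of the MACE SAP, which censors event-free subjects at the last contact where every component of the outcome was assessed.

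Separately, the protocol's repeat-test trigger does not match the endpoint it would help to confirm.

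**Working it through.** The documents state no event rate, discontinuation rate or power for this endpoint, so there is no figure to reproduce. Every rate below is an assumption.

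**1. Effect of the censoring rule.** Let *l* be the hazard of the eGFR components, *m* that of dialysis or transplant, *d* that of discontinuation, and F = 2 years (the MACE SAP expects mean follow-up of about 2 years). All hazards are constant and independent, and eGFR events are visible only before discontinuation.

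- Full observation: P = 1 − exp(−(l+m)F).
- SAP rule, probability of no recorded event: S = exp(−mF) × [1 − l/(l+d) × (1 − exp(−(l+d)F))].
- SAP rule, person-years: PT = d/(l+d) × (1 − exp(−mF))/m + l/(l+d) × (1 − exp(−(l+d+m)F))/(l+d+m).
- Recorded rate = (1 − S)/PT. The ratio of these rates stands in for the Cox hazard ratio.

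Worked case, true ratio 1.30:

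- Control (l = 0.10, m = 0.05, d = 0.15): S = 0.9048 × (1 − 0.40 × 0.3935) = 0.7624, so 0.2376 have a recorded event. Full observation gives 1 − exp(−0.30) = 0.2592, and 0.2376/0.2592 = 0.917, so 8% go uncounted. PT = 0.60 × 1.9033 + 0.40 × 1.5040 = 1.7435. Rate = 0.1363.
- Vadadustat (l = 0.13, m = 0.065, d = 0.30): S = 0.8781 × (1 − 0.3023 × 0.5768) = 0.7250, so 0.2750 have a recorded event. PT = 0.6977 × 1.8755 + 0.3023 × 1.2695 = 1.6923. Rate = 0.1625.
- Ratio = 0.1625/0.1363 = 1.19 instead of 1.30. With follow-up ended at the last eGFR, the rates are l + m in each arm: 0.195/0.15 = 1.30.

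Range over (l, m) = (0.10, 0.05), (0.15, 0.10) and (0.20, 0.05):

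| Discontinuation per year | True 1.00 appears as | True 1.30 appears as |
|---|---|---|
| Equal (0.15 or 0.30 in both arms) | 1.00 | 1.30 |
| Vadadustat 0.30, control 0.15 | 0.90–0.93 | 1.16–1.21 |
| Vadadustat 0.15, control 0.30 | 1.08–1.11 | 1.40–1.45 |

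Between 7% and 18% of an arm's progression events go uncounted.

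**2. Discontinuation related to renal risk.** Now let one gamma frailty (variance 0.5) raise all three hazards, with l = 0.15, m = 0.07 and d = 0.30 for vadadustat against 0.15 for control, over 2 years. A full-observation ratio of 1.18 becomes 1.08 under the SAP rule and 1.13 with follow-up ended at the last eGFR; 1.00 becomes 0.91 and 0.95. With variance 1.0, 1.17 becomes 1.07 and 1.09. The change helps but is partial.

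**3. Confirmation.**

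- Scheduled eGFR after Week 52 falls at Weeks 76, 104, 128, 156, 180 and 208, so gaps are 24 or 28 weeks (168 or 196 days), against 30 to 60 days with the repeat test. In Year 1 the gaps are 4 to 8 weeks.
- SAP 6.3.6 sets a minimum interval and no maximum, so the next scheduled eGFR can confirm a fall of 40% to 49%.
- The below-15 component is also unmatched. The fall needed is 1 − 15/baseline: 25% from a baseline of 20, 40% from 25, 50% from 30. For baselines under 30 it is reached before the trigger.

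**The case against.** The strongest case on the other side has five parts.

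- **Off-drug eGFR may exist.** Protocol 11.5 keeps planned assessments going, protocol 10.1.1 and the schedule footnotes say the same for transplanted and pregnant subjects, and SAP 5.1 would use any later value. This stands as an unresolved conflict. It does not rescue the rule: ending follow-up at the last evaluable eGFR suits either reading and changes little if off-drug samples are collected.
- **Confirmation is not simply lost.** The End of Treatment visit includes creatinine and eGFR, and is held at discontinuation or at study closure. Stopping drug can therefore supply the confirming value. This stands. A reader might infer that the 50% trigger misses the 40% endpoint; it does not, because scheduled and End of Treatment samples can confirm it. The real losses are deaths before the next sample, missed End of Treatment visits, and falls first seen at that visit or within 28 days of it.
- **Direction is unknown.** A reader might infer that renal harm from vadadustat is hidden. That needs vadadustat subjects to stop more often, and the documents give no rates; the reverse imbalance creates apparent harm. Counting errors also do not all run one way: eligibility has no lower eGFR limit and SAP 11 has a subgroup below 15, whose members meet that criterion from the start unless excluded.
- **The remedy is imperfect.** It gives up later dialysis and transplant, and step 2 shows residual bias when discontinuation tracks renal risk. This stands, and is the reason for the companion analysis.
- **The consequence is limited.** SAP 9.3 treats this as exploratory without multiplicity control, Appendix E.1.5 tabulates unconfirmed 40% falls, and chronic dialysis is always a serious adverse event, reported to global study completion. So off-drug subjects are not unobserved; only the eGFR components go dark. This stands too, although the E.1.5 table gives no hazard ratio and, under SAP 2.2, also ends with treatment.

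**Conclusion.** The censoring rule does not fit the endpoint. On the SAP 2.2 reading, off-drug time is counted as progression-free for two components that are no longer measured. Under constant, independent hazards, a twofold difference in discontinuation moves the ratio by roughly 7% to 11%, in a direction set by which arm stops more. With equal discontinuation the ratio is essentially unbiased and only events are lost. All these sizes rest on assumed rates.

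The repeat-trigger mismatch is a smaller matter: it delays confirmation by up to 24 to 28 weeks after Week 52 and loses some events. Primary efficacy and MACE conclusions are untouched. The rule should be corrected before unblinding, while the direction of any imbalance is still unknown.

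**What to change.** - **SAP D.3:** end composite follow-up for every subject at the last evaluable eGFR, the last time all components were assessed. Dialysis or transplant after that date does not count in the composite. Applying the cut-off only to subjects without progression, while keeping late dialysis as events, would introduce its own bias: a true 1.00 came out at 1.05 in simulation with independent discontinuation. State also that a sample drawn after dialysis starts still counts as an assessment for the cut-off; otherwise on-treatment dialysis could always fall after it.
- **Companion analysis:** time to dialysis or transplant alone, followed to end of study. This needs protocol 10.1.1 reconciled, since one paragraph says transplants are not recorded as adverse events and another makes them always serious.
- **Off-drug assessments:** reconcile protocol 11.5 with SAP 2.2 and protocol 7.5.5.4.
- **Repeat test:** reconcile the 50% trigger in protocol 9.2.2 with the SAP 6.3.6 definition.

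The cost is a rewritten SAP sentence, one added analysis and text reconciliation, with some extra creatinine samples if the trigger changes. Later dialysis and transplant leave the composite and appear only in the companion analysis, and some bias remains if discontinuation is related to renal risk.
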